7.2.2 Modified Mayo Score and Partial Mayo Score

The modified Mayo Score is defined as the Mayo Score without the PGA and ranges from 0 to 9. The partial Mayo Score is defined as the Mayo Score without the endoscopy subscore and ranges from 0 to 9.

Endpoints based on the Mayo Scores are defined below:

- Clinical remission: modified Mayo Score (SF subscore ≤ 1 [with or without decrease], RB subscore of 0, and endoscopic subscore of ≤ 1 [where the definition of 1 does not include friability])
- Clinical response (based on the modified Mayo Score): decrease in modified Mayo Score of ≥ 2 and a relative $\geq 30\%$ decrease from baseline, and a decrease of the Mayo RB subscore of at least 1 point or an absolute subscore for RB of 0 or 1

- Clinical response (based on the partial Mayo Score): decrease in partial Mayo Score of ≥ 2 .

Note: the clinical response based on the partial Mayo Score will be used in the decision to taper steroid (as applicable) at Week 24 for subjects in the OL phase.

- Endoscopic improvement: Mayo endoscopic subscore of less than or equal to 1
- Endoscopic remission: Mayo endoscopic subscore of 0
- Mucosal healing: Geboes index score < 2 and endoscopic remission (Mayo endoscopic subscore of 0)
- Symptomatic remission: SF subscore 0 or 1 with a decrease of ≥ 1 point from baseline, and RB subscore of 0
- Symptomatic response: $\geq 30\%$ decrease from baseline in composite sum of SF and RB subscores
- UC-100: Composite UC-100 score ($1 + 16 \times$ Mayo SF subscore [0 to 3] $+ 6 \times$ Mayo endoscopic subscore [0 to 3] $+ 1 \times$ RHI score [0 to 33]) ranges from 1 (no disease activity) to 100 (severe disease activity)

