2.2.3 Exploratory Endpoints

- Mean change from baseline in modified Mayo Score at Week 12
- Mean change from baseline in total Mayo Score at Week 12
- Mean change from baseline in partial Mayo Score at Weeks 2, 4, 6, 8, 10, and 12
- Mean change from baseline in Roberts Histopathology Index (RHI) score at Week 12
- Mean change from baseline in UC-100 score at Week 12
- Mean change from baseline in fecal calprotectin (FC) at Weeks 4 and 12
- Mean change from baseline in high sensitivity C-reactive protein (hs-CRP) levels at Weeks 2, 4, 8, and 12
- Mean change from baseline in patient-reported outcome (PRO) measures at Week 12
 - Inflammatory Bowel Disease Questionnaire (IBDQ)
 - Short Form-36 (SF-36)
- Proportion of subjects achieving clinical remission at Week 12
- Proportion of subjects achieving endoscopic improvement at Week 12
- Proportion of subjects achieving clinical response at Week 12
- Proportion of subjects achieving symptomatic remission at Weeks 2, 4, 6, 8, 10, and 12
- Proportion of subjects achieving symptomatic response at Weeks 2, 4, 6, 8, 10, and 12
- Proportion of subjects achieving endoscopic remission at Week 12
- Proportion of subjects achieving histologic remission at Week 12
- Proportion of subjects achieving histologic response at Week 12
- Proportion of subjects achieving mucosal healing at Week 12
- Change from baseline in partial Mayo Score beyond Week 12
- Incidence and characterization of TEAEs and laboratory abnormalities beyond Week 12
- Changes in PT101- and UC-associated biomarkers

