4.1 Inclusion Criteria

1. Male or female, 18 to 80 years of age, inclusive.
2. Diagnosis of UC at least 3 months prior to screening; diagnosis must be confirmed by endoscopy during the screening period. Source documentation of biopsy results (e.g., histopathology report) and endoscopic evidence consistent with the diagnosis of UC in the assessment of the Investigator is required.
3. Active UC as follows: subjects with mildly to severely active UC (i.e., 3-component modified Mayo Score of 4 to 9, with a rectal bleeding subscore of ≥ 1 , stool frequency subscore of ≥ 1 , and endoscopic subscore ≥ 1 excluding physician global assessment [PGA] subscore) and PGA score ≥ 1 .

*Note: The stool frequency (SF) and rectal bleeding (RB) Mayo subscores must be calculated based on the subject's Mayo Score diary data recorded over the **3 consecutive days prior to the endoscopy** (excluding the bowel preparation day; see [Section 7.2.1](#) and [Appendix 3](#)).*

4. Inadequate response, loss of response, or intolerance to at least 1 prior conventional therapy, and no more than 2 prior advanced therapies.
 - **Conventional Therapies**
 - Oral 5-aminosalicylates
 - Rectal corticosteroids
 - Oral and/or intravenous (IV) corticosteroids
 - Oral thiopurines
 - **Advanced therapies:**
 - Biologic therapy (e.g., anti- tumor necrosis factor-alpha (TNF- α), anti-integrin, anti-interleukin therapies)
 - Janus kinase (JAK) inhibitors
 - Sphingosine-1-phosphate receptor 1 (S1P1) inhibitors
5. Subjects at risk for colorectal cancer must have a colonoscopy prior to or at screening as follows:
 - Subjects > 50 years of age must have documentation of a colonoscopy within 3 years of the screening visit to exclude adenomatous polyps. Subjects whose adenomas have been completely excised at screening are eligible.
 - Subjects with extensive colitis for ≥ 8 years, or disease limited to the left side of the colon for ≥ 10 years, must either have had a full colonoscopy to assess for the presence of dysplasia within 1 year before first administration of study drug or a full colonoscopy to assess for the presence of malignancy at the screening visit.
6. Meets the following tuberculosis (TB) screening criteria:
 - No evidence of active TB, latent TB, or inadequately treated TB as evidenced by 1 of the following:
 - Negative QuantiFERON test or equivalent assay reported by the central lab at screening or within 90 days prior to randomization date, OR

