7.2 Response/Efficacy Assessments

7.2.1 Mayo Score

The Mayo Score is an instrument designed to measure disease activity in patients with UC. The Mayo Score ranges from 0 to 12 points and consists of the following 4 subscores, each graded from 0 to 3, with higher scores indicating more severe disease (see [Appendix 3](#)).

- Stool frequency (SF)
- Rectal bleeding (RB)
- Findings of flexible sigmoidoscopy
- Physician global assessment (PGA)

Calculation of the SF and RB subscores requires an assessment of the subject's bowel movement frequency and quantification of the amount of blood in the stool. The SF and RB Mayo subscores will be calculated based on the subject's Mayo Score diary data recorded in the week prior to the endoscopy (for modified Mayo Score) or prior to the visit (for partial Mayo Score) (see [Section 7.2.1.1](#) for eDiary instructions and review).

The mucosal appearance during the sigmoidoscopic/colonoscopic portion of the endoscopic examination will be assessed for calculation of the Mayo endoscopic subscore based on the scoring system provided in [Appendix 3](#). The endoscopic appearance will be read by both the Investigator and a central reader. Additional details are provided in the Central Imaging Management Solutions manual. Centrally read endoscopic subscores will be used for both IBT eligibility and the efficacy analyses. The Investigator-read endoscopic subscores will be used to assess eligibility for the OL and CBT phases.

The PGA subscore is assessed by the Investigator and is recorded at all study visits. The endoscopic subscore and the PGA must be performed by a physician qualified to perform

endoscopy. It is recommended that the same physician performs all such assessments for a particular subject throughout the study.

7.2.1.1 eDiary Instructions and Review

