7.2.3.2 Robarts Histopathology Index

The RHI is a recently validated instrument that measures histological disease activity in patients with UC (see [Appendix 5](#)). The RHI is divided into 4 categories: chronic inflammatory infiltrate, lamina propria neutrophils, neutrophils in epithelium, and erosion or ulceration (each ranging from 0–4). The RHI is comparable to, and often correlates with the Geboes score.

Endpoints based on the GS and RHI are defined below:

- Histologic remission: Geboes index score $< 2B.1$ or RHI score ≤ 3 , with subscores of 0 for lamina propria neutrophils and 0 for neutrophils in epithelium

- Histologic response: change from baseline RHI ≥ 7 points
- Mucosal healing: Histologic remission (as defined by the Geboes or RHI score) and endoscopic remission (Mayo endoscopic subscore of 0)
- UC-100: Composite UC-100 score ($1 + 16 \times$ Mayo SF subscore [0 to 3] $+ 6 \times$ Mayo endoscopic subscore [0 to 3] $+ 1 \times$ RHI score [0 to 33]) ranges from 1 (no disease activity) to 100 (severe disease activity) (see [Appendix 6](#))

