**Table 5. Definition of Binary Endpoints**

Binary Endpoint	Measure	Definition	Analysis Timepoint
Clinical Remission	Modified MCS	Modified MCS (SF subscore $\leq 1$ [with or without decrease], RB subscore of 0, and MES of $\leq 1$ [where the definition of 1 does not include friability])	CCI
Endoscopic Improvement	MES	MES of less than or equal to 1	
Clinical Response	Modified MCS	Decrease in modified MCS of $\geq 2$ and a relative $\geq 30\%$ from baseline, and a decrease of the Mayo RB subscore of at least 1 point or an absolute subscore for RB of 0 or 1	
Symptomatic Remission	SF, RB	SF subscore 0 or 1 with a decrease of $\geq 1$ point from baseline, and RB subscore of 0	
Symptomatic Response	SF, RB	$\geq 30\%$ decrease from baseline in composite sum of SF and RB subscores	
Endoscopic Remission	MES	MES of 0	
Histologic Remission	GHI, RHI	Geboes index score $< 2B.1$ or RHI score $\leq 3$ , with subscores of 0 for lamina propria neutrophils and 0 for neutrophils in epithelium	
Histologic Response	RHI	Change from baseline RHI $\geq 7$ points	
Mucosal Healing	GHI, MES	GHI $< 2$ and endoscopic remission (MES of 0)	

GHI = Geboes histologic index; MCS = Mayo score, MES = Mayo endoscopic subscore; RB = rectal bleeding; RHI = Robarts Histopathology Index; SF = stool frequency

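### Endoscopic improvement needs no improvement: subjects admitted with a Mayo endoscopic subscore of 1 already meet it before dosing

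*Protocol*

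**What the plan says.** **Entry.** Inclusion criterion 3 (Protocol 4.1 and synopsis) asks for a "3-component modified Mayo Score of 4 to 9", with rectal bleeding (RB) and stool frequency (SF) each at least 1, "and endoscopic subscore ≥ 1 excluding physician global assessment". MES 1 is therefore allowed whenever SF + RB is 3 or more.

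**Endpoint.** Protocol 7.2.2 gives "Endoscopic improvement: Mayo endoscopic subscore of less than or equal to 1". SAP Table 5 gives "MES of less than or equal to 1". Protocol 2.2.3 lists it as "Proportion of subjects achieving endoscopic improvement at Week 12". None of these mentions a change from baseline.

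**Reader and baseline.** Protocol 7.2.1 states: "Centrally read endoscopic subscores will be used for both IBT eligibility and the efficacy analyses". SAP 6.1.1.4 takes the screening MES as baseline, because no endoscopy is done on Day 1.

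**Analysis.** SAP 4.2.1 analyses all efficacy endpoints in all randomized subjects. SAP 6.2.1.1 and 6.2.4.1 impute missing assessments as non-response. Randomization is stratified by prior advanced therapy use only (Protocol 3.1). SAP 6.2.3 names baseline MES as a covariate that may enter a logistic model, and SAP 11 plans no subgroup analysis. SAP 5.3 summarises baseline MES by treatment group.

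**The concern.** The endpoint's name and the exploratory objective it serves (Protocol 2.1.3) are both about improvement. As defined, it is a threshold that part of the admissible population already sits under, so no change can be reported as success. The rate in each arm then depends partly on how many MES-1 subjects that arm happened to enrol. With 8 PT101 and 2 placebo subjects per cohort, and no stratification on MES, balance cannot be relied on. Subjects who already qualify also cannot show a drug effect on this endpoint except by avoiding worsening, so they dilute any difference between arms.

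SAP Table 6 has no continuous endpoint for change in MES alone. Endoscopic improvement and endoscopic remission are therefore the only stand-alone endoscopic readouts, and their raw rates are likely to be read directly.

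**Working it through.** The documents give no expected rate or power for this endpoint, so there is no figure to reproduce.

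**Step 1: who can enter already meeting the endpoint.** With SF, RB and MES each 1 to 3 there are 3 × 3 × 3 = 27 patterns. Only (1,1,1), sum 3, falls below the minimum total of 4, leaving 26. Patterns with MES 1 number 3 × 3 − 1 = 8, and all 8 satisfy MES ≤1 at screening. This counts patterns; it does not estimate prevalence.

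The friability qualifier does not help. Protocol Appendix 3 scores any friability as 2, at screening and at Week 12 alike.

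**Step 2: the other Mayo-based binary endpoints.** On screening values, none can be met at entry. Clinical remission and symptomatic remission need RB 0, while entry needs RB ≥1. Endoscopic remission and mucosal healing need MES 0, while entry needs MES ≥1. Clinical response and symptomatic response require a decrease. Endoscopic improvement is the exception.

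**Step 3: rate when nobody changes.** Let q be the share with baseline MES 1. The documents do not give it; 10%, 20% and 30% are assumed. With Week 12 reads available:

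- current definition: rate = q
- with a decrease of at least 1 point required: rate = 0

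If only 90% of MES-1 subjects have a Week 12 read at or below 1, their contribution is 0.9q, that is 9%, 18% or 27%.

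The chance that an arm of n holds at least one such subject is 1 − (1 − q)^n.

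| Assumed q | No-change rate, current | No-change rate, decrease required | At least 1 of 8 PT101 | At least 1 of 2 placebo |
|---|---|---|---|---|
| 10% | 10% | 0% | 57% | 19% |
| 20% | 20% | 0% | 83% | 36% |
| 30% | 30% | 0% | 94% | 51% |

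One unchanged MES-1 subject adds 1/8 = 12.5 points to a PT101 arm. It adds 1/2 = 50 points to one cohort's placebo group, or 1/6 = 16.7 points if placebo is pooled over the three planned cohorts.

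**Step 4: effect on the treatment difference.** For illustration, assume that 40% (PT101) and 10% (placebo) of subjects with baseline MES 2 or 3 reach MES ≤1, and that every MES-1 subject stays at or below 1.

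- Current: [q + (1 − q) × 0.40] − [q + (1 − q) × 0.10] = 0.30 × (1 − q).
- Decrease required, all subjects kept: 0.30 × (1 − q) + q × d, where d is the drug effect on moving from MES 1 to 0.
- Restricted to baseline MES ≥2: 0.40 − 0.10 = 0.30.

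| Assumed q | Current (PT101 − placebo) | Decrease required, nobody moves from 1 to 0 | Baseline MES ≥2 only |
|---|---|---|---|
| 10% | 46 − 19 = 27 | 36 − 9 = 27 | 40 − 10 = 30 |
| 20% | 52 − 28 = 24 | 32 − 8 = 24 | 40 − 10 = 30 |
| 30% | 58 − 37 = 21 | 28 − 7 = 21 | 40 − 10 = 30 |

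Requiring a decrease corrects the rate in each arm. With d = 0 it does not restore the difference; only the restricted denominator does.

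**The case against.** The best defence is that little depends on this endpoint. It is one of many exploratory endpoints. Protocol 9.3.4 calls the analyses descriptive, and the primary endpoint is safety. SAP 13 says only that these results may be given to the DRC, and selection for future development rests on safety and efficacy data taken together. No decision rule uses endoscopic improvement. Randomization means MES-1 subjects create no systematic bias towards PT101, and the 50-point swing in placebo reflects a group of two, where any single outcome moves the rate by 50. Baseline MES by arm and the by-subject listings would let a careful reader find the unchanged subjects. All of this stands and limits the consequence. None of it changes who is counted as improved.

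Four stronger readings are tempting, and the documents do not support them.

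- **That some subjects will in fact enter already meeting the endpoint.** The documents show only that they may; q is unknown.
- **That the sponsor closed this same gap for stool frequency**, since symptomatic remission requires "SF subscore 0 or 1 with a decrease of ≥ 1 point from baseline". That endpoint also requires RB 0, which no eligible subject has on screening values, so there was no such gap to close. The documents give no reason for the clause, and clinical remission in the same section explicitly accepts SF ≤1 without a decrease.
- **That adding the decrease clause alone cures dilution.** Step 4 shows otherwise when d = 0.
- **That histologic remission has a defect of the same size.** Entry sets no histologic activity floor, so a subject could already be in histologic remission at screening. Nothing in the documents allows this to be sized, and central scoring of biopsies is not stated.

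**Conclusion.** The point holds for endoscopic improvement. Following the plan as written labels an unchanged MES-1 subject with a Week 12 read as improved, and the optional MES covariate does not alter that. The defect follows from the text alone. Its size does not: the no-change rates of 10%, 20% and 30% are simply the assumed shares at MES 1, and the loss from 30 points to 27, 24 or 21 also rests on the assumed 40% and 10% rates and on all MES-1 subjects staying at or below 1. It is worth correcting because the remedy is cheap and uses data already collected. It does not threaten the primary or secondary objectives. For histologic remission, the documents support no more than a request to show how many subjects were already in remission at screening.

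**What to change.** In Protocol 7.2.2 and SAP Table 5, define endoscopic improvement as MES ≤1 at Week 12 with a decrease of at least 1 point from the screening central read. This sets the no-change rate to 0% in every arm.

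Also report the proportion with MES ≤1 among subjects with baseline MES ≥2, and show the number of baseline MES-1 subjects by arm next to both results. For histologic remission, show the number already meeting the definition at screening.

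**Cost.** Two definition lines and some programming. No new data are needed for the MES changes, because the screening subscore is already read centrally. Entry to the later treatment phases depends on clinical response, so subject routing is unaffected. Reported rates will be lower, the restricted version has a smaller denominator than the SAP's all-randomized set, and the definition will differ from the plain MES ≤1 threshold. That plain proportion can still be shown alongside, labelled as a threshold and not as improvement.

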7.2.3 Geboes Score and Robarts Histopathology Index

7.2.3.1 Geboes Score

The original Geboes score (GS) is the most commonly used colon mucosal histological score in the UC field. It is divided into 6 grades: architectural changes (Grade 0), chronic inflammatory infiltrate (Grade 1), lamina propria neutrophils and eosinophils (Grade 2), neutrophils in epithelium (Grade 3), crypt destruction (Grade 4) and erosions or ulcerations (Grade 5), and each grade of the score is divided in 4 subcategories (see [Appendix 4](#)). The Geboes score ranges from 0 to 5.4, with higher scores indicating more severe inflammation; typically, UC is defined as active histological inflammation with a Geboes score of $\geq 2B.1$ ([Ma, 2021](#)).

7.2.3.2 Robarts Histopathology Index

The RHI is a recently validated instrument that measures histological disease activity in patients with UC (see [Appendix 5](#)). The RHI is divided into 4 categories: chronic inflammatory infiltrate, lamina propria neutrophils, neutrophils in epithelium, and erosion or ulceration (each ranging from 0–4). The RHI is comparable to, and often correlates with the Geboes score.

Endpoints based on the GS and RHI are defined below:

- Histologic remission: Geboes index score $< 2B.1$ or RHI score ≤ 3 , with subscores of 0 for lamina propria neutrophils and 0 for neutrophils in epithelium

- Histologic response: change from baseline RHI ≥ 7 points
- Mucosal healing: Histologic remission (as defined by the Geboes or RHI score) and endoscopic remission (Mayo endoscopic subscore of 0)
- UC-100: Composite UC-100 score ($1 + 16 \times$ Mayo SF subscore [0 to 3] $+ 6 \times$ Mayo endoscopic subscore [0 to 3] $+ 1 \times$ RHI score [0 to 33]) ranges from 1 (no disease activity) to 100 (severe disease activity) (see [Appendix 6](#))

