## 4 GENERAL CONSIDERATIONS FOR DATA ANALYSIS

### 4.1 REPORTING CONVENTIONS

The summary tables, figures, and by-subject listings will be prepared using the following conventions:

- Unless otherwise specified, the baseline value is defined as the last non-missing assessment prior to the first dose of study treatment. The last non-missing evaluation includes unscheduled and repeat visits.
- If the date of interest occurs on or after the first dose/randomization date, the study day will be calculated as “date of interest – date of first dose/randomization + 1”.
- If the date of interest occurred prior to the first dose/randomization date, then study day will be calculated as “date of interest – date of first dose/randomization”.
- Both safety and efficacy analysis results will be presented using descriptive statistics. Depending on the parameter, the difference from baseline will either be computed using the original scale (raw change from baseline) or on the log scale and back transformed for reporting.
- Categorical data will be summarized by treatment group in terms of frequency counts and percentages.
- Continuous variables will be summarized by treatment group using descriptive statistics (the number of subjects [n], mean, median, SD, minimum, and maximum) of the values at each visit and the change from baseline to each visit. PK parameters and other laboratory analytes that are believed to follow an

approximate log-normal distribution will also be summarized by the geometric mean and coefficient of variation (expressed as a percent).

- CIs will be presented as 2-sided 95% CIs.
- All mean, median, and CI values will be formatted to one more decimal place than the measured values. SD values will be formatted to two more decimal places than the measured value. Minimum and maximum will be formatted to the same number of decimal places as the measured value. The maximum number of decimal places reported shall be four for any summary statistic.
- All percentages will be rounded to one decimal place. The number and percentage of responses will be presented in the form XX (XX.X), where the percentage is in the parentheses.
- Change from baseline is calculated as a post-baseline value minus the baseline value.
- All laboratory data will be reported using standard international units.
- All analyses and summary tables will include the analysis set sample size (i.e., number of subjects) in the column headings.

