### 6.1.3 ROBARTS HISTOPATHOLOGY INDEX

The Robarts Histopathology Index (RHI) measures histological disease activity in patients with UC ([Appendix D](#)). The RHI is divided into 4 categories: 1) the extent of chronic inflammatory cell infiltration, 2) neutrophils in the lamina propria, 3) neutrophils in the epithelium, and 4) erosions and ulceration. Each item has 4 levels and is scored from 0 to 3 and multiplied by a weighting factor and summed to give the overall RHI score. The RHI score ranges from 0 to 33, with higher scores being indicative of more severe disease. If any one component of the RHI is found to be missing, then the overall RHI score will be set as missing. The equation used to calculate the RHI is shown below.

**RHI** = 1 x chronic inflammatory infiltrate level + 2 x lamina propria neutrophils + 3 x neutrophils in epithelium + 5 x erosion or ulceration\*

\*A Geboes Grade 5 component score of  $>1$  is reduced by 1 point prior to be incorporated into the RHI calculation.

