**Table 6. Definition of Continuous Efficacy Endpoints**

Measure	Definitions	Analysis Timepoint
mMCS	Mean changes in mMCS from baseline	CCI
MCS	Mean change in total MCS	
pMCS	Mean changes in pMCS from baseline	
RHI	Mean change in RHI from baseline	
UC-100	Mean change in UC-100 score from baseline	
pMCS	Mean changes in pMCS from baseline	

MCS = Mayo Score; mMCS = modified Mayo score; pMCS = partial Mayo Score; RHI = Robarts Histopathology Index; UC = ulcerative colitis

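### Histologic response is a change in RHI of at least 7 points with no direction; under the SAP's sign rule this counts worsening as response

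*Protocol*

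**What the plan says.** Protocol 7.2.3.2 reads "Histologic response: change from baseline RHI ≥ 7 points". SAP Table 5 has the same rule: "Change from baseline RHI $\geq 7$ points". Neither says whether the change is a fall or a rise.

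Two other SAP statements settle how the rule would be computed. Section 4.1 (Reporting Conventions): "Change from baseline is calculated as a post-baseline value minus the baseline value", with no exception for RHI. Section 6.1.3: "The RHI score ranges from 0 to 33, with higher scores being indicative of more severe disease".

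The sibling response endpoints do give a direction. Clinical response in Protocol 7.2.2 is a "decrease in modified Mayo Score of ≥ 2 and a relative" fall of at least 30%. Symptomatic response in SAP Table 5 is a 30% or greater "decrease from baseline in composite sum of SF and RB subscores". The RHI route to histologic remission is a low absolute score: "or RHI score ≤ 3 , with subscores of 0 for lamina propria neutrophils and 0 for neutrophils in epithelium". SAP section 14 (Changes from Protocol) does not mention histologic response.

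**The concern.** A threshold of at least +7 on a signed difference, on a scale where high is bad, picks out subjects who got worse. A table programmed from the SAP text would report the rate of histologic worsening under the label of response.

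The rule would also conflict with histologic remission, because a subject could not be in remission and be a responder. Non-responder imputation (SAP 6.2.4.1) would lose its purpose as well. It is meant to penalise missing data, but under the written rule it places a missing subject in the group that holds every improver.

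A programmer who notices the problem has to depart from the SAP text and choose a repair. Reading the rule as a decrease or as an unsigned change gives different rates whenever any subject worsens by 7 points or more.

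Histologic response is among the analyses that may be given to the DRC (SAP 13). Protocol 9.3.4 and SAP 13.1 say that the totality of Week 12 safety and efficacy data informs dose selection for later development. It is not itself a decision criterion.

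**Working it through.** **Inputs.** RHI = a + 2b + 3c + 5d, each item scored 0 to 3 (SAP 6.1.3 and Appendix D; Protocol Appendix 5). Change = post-baseline − baseline (SAP 4.1). Threshold 7 (Protocol 7.2.3.2, SAP Table 5). PT101 arm of 8 and 2 placebo subjects per dose level (Protocol 9.1).

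**Scale.** The maximum is 3 × (1 + 2 + 3 + 5) = 33, which reproduces the stated range. The 4⁴ = 256 item combinations yield every integer from 0 to 33, so there are 34 values and 34 × 34 = 1,156 baseline/Week 12 pairs. Protocol 7.2.3.2 also describes the items as running from 0 to 4, which would give 4 × 11 = 44. That contradicts the 0–33 range stated in both documents, so 0 to 3 is used here.

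**Pair counts.** The number of pairs with a rise of at least 7 is the sum over d = 7 to 33 of (34 − d) = 27 × 28 / 2 = 378. By symmetry, 378 pairs are falls of at least 7. The remaining 1,156 − 756 = 400 are neither.

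| Baseline → Week 12 | Change | As written (≥ +7) | Decrease (≤ −7) | Unsigned (≥ 7) |
|---|---|---|---|---|
| 20 → 5 | −15 | no | yes | yes |
| 5 → 20 | +15 | yes | no | yes |
| 33 → 0 | −33 | no | yes | yes |
| 10 → 3 | −7 | no | yes | yes |
| 27 → 33 | +6 | no | no | no |

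All 378 responders under the written rule are worsenings. None is also a responder under the decrease rule. The two rules agree only on the 400 pairs where both say non-response. The unsigned reading has 756 responder pairs, half of them worsenings.

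**Conflict with remission.** A responder under the written rule has Week 12 RHI of at least 0 + 7 = 7, so none can have RHI ≤ 3. Conversely, going from RHI ≥ 10 to ≤ 3 is a fall of at least 7 and is scored as non-response. The Geboes route gives the same result. A score below 2B.1, taken as the highest non-zero grade (SAP 6.1.2), means no neutrophils and no erosion, leaving only chronic infiltrate and RHI ≤ 3.

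**Ceiling.** The written rule needs baseline ≤ 33 − 7 = 26. Subjects with baseline RHI of 27 to 33, the most severe, can never respond.

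**Effect on a rate.** With k subjects falling and m rising by at least 7 in an arm of n, the intended rate is k/n, the written rate m/n and the unsigned rate (k + m)/n. The documents give no expected counts, so those below are assumed for illustration.

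- PT101, n = 8, k = 2, 4 or 6: intended 25%, 50% or 75%. With m = 0, 1 or 2 the written rate is 0%, 12.5% or 25%, whatever k is.
- k = 4, m = 1: intended 4/8 = 50%, written 1/8 = 12.5%, unsigned 5/8 = 62.5%.
- Against 6 placebo subjects (3 cohorts × 2, pooling assumed) with k = 1, the intended difference is 4/8 − 1/6 = +33.3 points. The written rule gives 1/8 − 2/6 = −20.8 points if placebo m = 2, and 1/8 − 0/6 = +12.5 points if placebo m = 0.

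**The case against.** The strongest reply is that the direction can be found elsewhere. Both documents list histologic response under the exploratory objective of improving disease activity, so worsening cannot sensibly count as response. The protocol gives no sign rule of its own, which leaves its definition undirected, not inverted. The inversion appears only when a reporting convention from SAP 4.1 is applied to it. The same objective makes the unsigned reading unlikely.

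This shows that a decrease was meant. It does not alter the rule that a programmer would code, because SAP 4.1 applies unless an exception is stated and none is.

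Several limits stand. The pair counts are unweighted and say nothing about how often patients would fall in each cell. Calling the 756 pairs misclassified presumes that a decrease is the true rule. The reversed treatment difference depends on invented counts.

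An inverted rate would probably be noticed, because by-subject listings are planned (SAP 6.2.1.1) and SAP Table 6 reports "Mean change in RHI from baseline". SAP 1.1 exempts cosmetic changes from the duty to document changes made after lock, and one could argue that supplying the evident direction is cosmetic. These points limit the consequence; they are not reasons to leave the text as it is.

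**Conclusion.** The concern holds. The protocol leaves the direction of histologic response undefined. The SAP, read with its own sign rule and scale direction, defines it the wrong way round. This is probably one wrong word, and a decrease was almost certainly intended.

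If coded as written, every improvement of at least 7 points is lost and every worsening of at least 7 points is counted. The reported rate becomes m/n instead of k/n. The logical result needs only the documents' own scoring and sign rules; the size in patients depends on counts that the documents do not give.

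The endpoint is exploratory and Protocol 9.3.4 describes these analyses as descriptive, so no primary or secondary conclusion is at risk. It should be corrected, but it does not threaten the trial.

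**What to change.** In SAP Table 5, define histologic response as a decrease from baseline in RHI of at least 7 points (post-baseline minus baseline ≤ −7), and record the clarification in SAP section 14. Put the same wording in Protocol 7.2.3.2. Protocol section 9 requires an amendment for an analysis change only when site conduct is affected, so the protocol line can wait for the next revision while the SAP is corrected now. No other endpoint needs to change.

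The cost is one line in each document plus the section 14 entry. No new data, visits or analyses are needed: biopsies are already taken at screening and Week 12 (Protocol 7.2.1.2), and change in RHI is already derived for SAP Table 6. Made before database lock, this is a wording edit. Made afterwards, it would have to be explained in the study report under SAP 1.1 unless it is accepted as cosmetic.
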